## 2.2 Analysis sets

**Safety set:** The Safety Set includes all patients who received at least one dose of study treatment.

All analyses will be performed using the Safety Set.

### **2.2.1 Subgroup of interest**

Summary tables can be analysed on the following prior RMS DMTs subgroups:

- Any Interferon Beta
- Glatiramer acetate
- Fingolimod patients (overall, with / without dose titration)
- Fumarates
- Teriflunomide
- Natalizumab
- Ocrelizumab

Population subgroups, Hispanic or Latino, Black or African American, White (excluding Hispanic or Latino), Hispanic or Latino (excluding white) [REDACTED] may also be performed based on clinical team's decision for analysis.

[REDACTED]

## **2.3 Patient disposition, demographics and other Baseline characteristics**

All the patient demographic and Baseline characteristics will be summarized for the Safety Set in the CSR.

### **2.3.1 Patient disposition**

Screening phase disposition and study phase disposition will be summarized.

The number and percentage of patients screened, screened passed and screen failed will be summarized for all the screened patients for the screening phase disposition.

For the study phase disposition, the overall number of patients who are screened passed i.e. entered into the study, completed the study and discontinued from the study (and/or treatment) will also be summarized with reasons for premature discontinuation on all enrolled patients.

Patient identification number and whether they completed or discontinued from the study (and/or treatment) will be listed, with date of last dose and primary reason for premature discontinuation.

For each protocol deviation (PD), the number and percentage of patients for whom the PD applies will be tabulated. A separate listing will be provided for the details on the patient identifier having met a specific PD.

The PD's will be distinguished in the below 5 categories as applicable:

- Selection Criteria Not Met - Inclusion/Exclusion criteria

- Patient Not Withdrawn As Per Protocol - Withdrawal criteria met but patient not withdrawn
- Treatment Deviation - Wrong treatment or incorrect dose
- Prohibited concomitant medication
- Other

### **2.3.2 Demographics and other Baseline characteristics**

The following common background, demographics and Baseline characteristics data will be analyzed as described below:

Continuous variables:

- Age (which is derived from date of birth and the screening assessment date)
- Height (cm)
- Weight (kg)
- Body Mass Index (BMI)

Categorical variables:

- Age group (<=30 years, 31 - <= 40 years, 41 - <=50 years, 51 - <=60 years, > 60 years)
- Gender
- Race
- Ethnicity

Multiple Sclerosis History and the expanded disability status scale will also be presented with all the parameters collected according to the eCRF.

The above characteristics will be repeated on the required subgroups.

Unless otherwise specified, summary statistics will be presented for continuous variables for all patients (total) in the safety set. The number and percentage of patients in each category will be presented for categorical variables for all patients (total) in the safety set.

### **2.3.3 Medical history/current medical conditions**

Medical history will be coded using the Medical Dictionary for Regulatory Activities terminology (MedDRA, current version at database lock). History/conditions and current medical conditions at Baseline will be summarized for the safety set by primary system organ class and preferred term, and overall. Verbatim recorded history/conditions will be listed together with the coded terms, date of diagnosis/surgery and whether the problem was ongoing at start of the study.

## **2.4 Treatments (study treatment, rescue medication, concomitant therapies, compliance)**

### **2.4.1 Study treatment / compliance**

Duration of exposure to the study treatment (siponimod) will be calculated as the number of days exposed to the treatment with siponimod over the specified period (expressed as:

Duration of exposure = last known date of siponimod administration – first known date of siponimod administration + 1).

The duration of exposure (in days) will be summarized for the safety set as:

- a continuous variable with the standard descriptive statistics, and
- a categorical variable classified into <=4 weeks, >4 to <=8 weeks, >8 to <=12 weeks, >12 to <=16 weeks, >16 to <=20 weeks and >20 to <=24 weeks.

A data listing of the drug doses administered by patients will be provided.

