6.1 Study treatment

6.1.1 Investigational and control drugs

Chemical Name: Siponimod

Other Names: BAF312, Mayzent ®

Classification: Oral sphingosine 1-phosphate receptor modulator

The investigational drug siponimod will be provided as film coated tablets. Please refer to the pharmacy manual provided for specific instructions.

The study medication will be administered orally, once daily, with or without food.

Should titrated patient miss one day of titration or more, the patient will need to restart the titration with Day 1 dosing (0.25mg), including Day 1 cardiac assessments (pre-dose ECG and 6-hour post dose heart rate). It is strongly recommended, during the titration phase, that a member of the study staff contact the patient, once daily via phone, to remind them to take their study medication as required. This is because restarting the titration will require the patient to come in for an unscheduled visit to do a pre-dose ECG assessment and 6 hour post-dose heart rate (holter telemetry monitoring).

Furthermore, if maintenance treatment (2mg) is interrupted for 4 or more consecutive daily doses, treatment must be re-initiated with the 5-day titration, including pre-dose ECG and 6-hour post-dose heart rate (holter telemetry monitoring) at an unscheduled visit. Treatment interruptions for up to 3 missed consecutive daily doses does not require re-titration, and treatment should be continued at the maintenance dose level.

If the patient has missed greater than 30 consecutive days of treatment, using his/her best medical judgement, the PI should consider terminating the patient from the study.

Treatment arm	# of patient's	Type of study drug	Compound	Min. Dose	Max. Dose	Frequency	Formulation	Admin Route	Generic acceptabl e
Arm 1	300 - 400	Investigational	Siponimod	0.25 mg	2 mg	Daily	Tablet	Oral	No

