- During all other study visits, outside of Day 1 (screening, V2, V3, V4 and V5) a qualified study personnel, as determined by the PI, will assess the patient's heart rate.
- Patients will then follow the normal visit schedule in the treatment period and should complete all of the relevant assessments as indicated in Table 8-1.

Patients should have all visits/assessments as outlined in the Assessment schedule Table 8-1 or as close to the designated day/time as possible with an allowed visit window of ± 3 days for visit 1 (BSL), an allowed visit window of ± 5 days for visits 2, 3, 4, 5 and an allowed ± 7 days for the 30-day telephone follow-up. Missed or rescheduled visits should not lead to automatic

Patients who prematurely discontinue the study for any reason should be scheduled for a visit as soon as possible, at which time all of the assessments listed for the final visit will be performed. At this final visit, all dispensed investigational product should be reconciled, and the adverse event and concomitant medications recorded on the eCRF.

End of Treatment/Study (EOT/S) Visit Schedule

discontinuation.

For patients who complete the core treatment period of the study, the end of treatment/study visit should be conducted. No study drug should be taken on the day of EOT/S.

For patients who discontinue study medication prematurely in the core treatment period, the end of treatment/study visit should be conducted when they stop taking study medication.

A follow-up telephone call, 30 days after the end of treatment/study visit, will be conducted for all patients who randomize.

As per Section 4.6, during a Public Health emergency as declared by Local or Regional authorities i.e. pandemic, epidemic or natural disaster that limits or prevents on-site study visits, alternative methods of providing continuing care may be implemented by the investigator as the situation dictates. If allowable by a local Health Authority and depending on operational capabilities, phone calls, virtual contacts (e.g. tele consult) or visits by site staff/ home nursing staff to the participant's home, can replace on-site study visits, for the duration of the disruption until it is safe for the participant to visit the site again.

Table 8-1 Assessment Schedule

Period	Scree	ening	Treatment			End of Treatment/St udy	Follow-up	Unplanned
Visit	Screening	Baseline ¹	Titration Treatment Period			End of Treatment/St udy	Safety	Unscheduled Visit

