### 2.1.1.2 Study day

Study day is defined with respect to the first day on which treatment with Siponimod starts. The date of first administration of study medication is defined as Day 1 and the day before is defined as Day -1.

Therefore, for any particular date, study day will be calculated as follows:

- For dates on or after the first date of study medication administration,  
Study day = Assessment date – Date of first administration of study medication + 1;
- For dates prior to the first date of study medication administration,  
Study day = Assessment date – Date of first administration of study medication.

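### SAP 2.4.1 has no exposure category above 24 weeks, although in-window completers can exceed it, and its days-exposed variable counts days off drug

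*SAP*

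**What the plan says.** SAP 2.4.1 describes exposure as the "number of days exposed to the treatment with siponimod over the specified period" and then gives the formula: "Duration of exposure = last known date of siponimod administration – first known date of siponimod administration + 1". The result is summarized as a continuous variable and in six categories. The first is up to 4 weeks and the last two are ">16 to <=20 weeks and >20 to <=24 weeks". There is no open-ended top category.

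The SAP's definition of study day fixes the time origin: "The date of first administration of study medication is defined as Day 1". Protocol Table 8-1 puts Visit 5 at Day 168, and the text of Protocol Section 8 gives "an allowed visit window of ± 5 days for visits 2, 3, 4, 5". The end-of-treatment part of the same section adds: "No study drug should be taken on the day of EOT/S". SAP Table 1 maps Day 127 to Day 183 to Visit 5/EOS.

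On interruptions, Protocol 6.1.1 says "if maintenance treatment (2mg) is interrupted for 4 or more consecutive daily doses, treatment must be re-initiated with the 5-day titration", so the patient continues in the study after the gap. Beyond 30 consecutive missed days, the investigator is asked to consider termination. Protocol Appendix 3 also provides for interruption and possible re-initiation after confirmed low lymphocyte counts. Protocol 6.6.1 takes exposure from the start and stop dates in the Dosage Administration Record (DAR).

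**The concern.** There are two separate points about one variable.

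- **Coverage.** The top category ends at 168 days, the same number as the nominal Visit 5 day. The allowed tolerance runs past that day, so a patient who follows the protocol can have a duration for which the table has no row. All such patients are at the long end of exposure.
- **Meaning.** The words describe days on drug, but the formula gives elapsed time from first to last dose. The two agree only for a patient without a gap, and the protocol expects some patients to stop and restart.

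This is a safety study with a 6-month treatment period, and readers use the exposure table as context for the adverse event percentages. A table that does not add up, or that reports off-drug days as exposure, weakens that context.

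**Working it through.** **Inputs.** Top category limit: 24 weeks (SAP 2.4.1). Day 1 = first dose (SAP 2.1.1.2). Visit 5: Day 168 ± 5 (Protocol Table 8-1 and Section 8). No dose on the visit day (Protocol Section 8). SAP Visit 5 window: up to Day 183 (SAP Table 1).

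**Step 1: the plan's own limit.** 24 × 7 = 168 days, which equals the nominal Visit 5 day. The last category, >20 to <=24 weeks, holds 141 to 168 days.

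**Step 2: exposure by exit day.** Let *d* be the day of Visit 5, with dosing continued until the day before. The last dose is on Day *d* − 1, so

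exposure = (*d* − 1) − 1 + 1 = *d* − 1.

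| Visit 5 day | Exposure (days) | Weeks | Category |
|---|---|---|---|
| 163 | 162 | 23.14 | >20 to <=24 |
| 168 | 167 | 23.86 | >20 to <=24 |
| 169 | 168 | 24.00 | >20 to <=24 |
| 170 | 169 | 24.14 | none |
| 171 | 170 | 24.29 | none |
| 172 | 171 | 24.43 | none |
| 173 | 172 | 24.57 | none |
| 183 (end of SAP window) | 182 | 26.00 | none |

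Of the 11 permitted days (163 to 173), four (170 to 173) give a duration outside every category. If a dose is taken on the visit day against the instruction, exposure equals *d* and Day 169 joins them, making five of 11.

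**Step 3: effect of a gap.** Take a patient with Visit 5 on Day 168, so a span of 167 days, who misses *g* consecutive days and restarts. The formula returns 167 for every *g*; net exposure is 167 − *g*.

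| Gap *g* (days) | Formula | Net days | Overstatement *g* / (167 − *g*) |
|---|---|---|---|
| 3 | 167 | 164 | 1.8% |
| 4 | 167 | 163 | 2.5% |
| 14 | 167 | 153 | 9.2% |
| 30 | 167 | 137 | 21.9% |

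With the 30-day gap the patient is placed in >20 to <=24 weeks, while 137 days (19.57 weeks) belongs in >16 to <=20 weeks. A patient who stops for good is not affected, because the last dose date already marks the stop.

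**Step 4: would the compliance table show it?** The SAP gives no compliance formula. If compliance is days dosed divided by days in the span (an assumption), the 30-day gap gives 137/167 = 82%. That falls in the SAP's highest category short of overdose, 75% to 100%, so the categorical compliance table would not show the gap either.

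**The case against.** The best case against this is that little depends on it.

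- **No endpoint uses the categories.** The primary analysis is a patient proportion with an exact binomial interval on the Safety Set (SAP 2.5.2), and the plan has no exposure-adjusted rate. The continuous summary includes patients above 168 days, and its maximum would show them. All of this stands.
- **A first-to-last-dose span is a common definition of treatment duration, and the formula is stated openly.** This also stands. The span suits a safety reading too: the protocol notes that lymphocyte effects may last 3 to 4 weeks after the last dose, and the on-treatment period runs to 30 days after it. That justifies reporting the span, but not calling it days exposed.
- **Interruptions are visible elsewhere**, in DAR-based compliance, the dose listing, the table of adverse events requiring interruption, and deviation codes TRT01, TRT02 and TRT09. This is true in part. None of these corrects the exposure variable or summarizes days on drug.

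Some stronger readings are tempting, but the documents do not support them. A reader might infer that over a third of completers go unclassified. Four in 11 (36%) is a share of permitted days and becomes a share of patients only if exits are uniform over the window, whereas the protocol asks for visits as near the planned day as possible. A reader might infer that adverse event percentages lose part of their denominator, but that denominator is the Safety Set. Nor does the protocol accept interruptions of any length: there is no fixed maximum, but it expects at least 80% compliance in maintenance and lists non-compliance as a ground for discontinuing treatment. Four missed days is a re-titration threshold; the formula counts shorter gaps as well.

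**Conclusion.** Both points hold as defects in a descriptive table.

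**Coverage.** Completers seen on Day 170 to 173 are within the allowed window, have 169 to 172 days of exposure, and fit no category. The same is true of patients dosed until a later visit up to Day 183. Completers seen on Day 168 or 169 are classified. The table may therefore fail to sum to the Safety Set. The number affected cannot be obtained from the documents. This rests on visit days being counted from the first dose and on dosing continuing to the day before Visit 5.

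**Meaning.** For a patient who interrupts and restarts, the variable exceeds days on drug by exactly the length of the gap: 4 days in 167 for a short interruption, 30 in 167 for a long one. This enters both the continuous and the categorical summaries. The documents do not say how often interruptions are expected, so the effect on the study mean cannot be sized.

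Neither point changes the primary endpoint, its confidence interval or any adverse event denominator.

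**What to change.** In SAP 2.4.1:

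1. Add a >24 weeks category, so that every duration has a row.
2. Label the present variable as time from first to last dose and keep its formula.
3. Add exposure net of interruption days, calculated from DAR start and stop dates, with the same continuous and categorical summaries.
4. State that the net figure removes only gaps recorded in the DAR. Isolated missed tablets known only from pill counts in source documents may remain.

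The cost is one table row, one label and one derived variable with its summary. No new data are needed, and nothing changes in patient conduct or in the primary analysis.

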#### **Investigator reported compliance from eCRF**

Compliance will be calculated based on the DAR data. Compliance data will be summarized descriptively as a continuous and categorical variable.

The number and percentages of patients in each of the compliance categories mentioned in the eCRF, i.e., Poor (< 25%), Average ( $\geq 25\%$  to < 50%), Good ( $\geq 50\%$  to < 75%), Very good ( $\geq 75\%$  to  $\leq 100\%$ ) and Overdose or misuse (>100%) will be summarized. In case of over compliance (> 100%) the reason will be listed.

The compliance will be provided for overall study period, titration and maintenance phase.

The exposure will be presented for the overall population along with the subgroups, if needed.

#### **2.4.2 Prior, concomitant and post therapies**

Each medication has the start and end dates recorded. Prior medications are defined as those medications which were taken and stopped prior to the first dose of study drug. Concomitant medications are defined as those medications which were taken on or after the first dose of study drug but not prior to the first dose of study drug. Prior/concomitant medications are defined as those medications which were taken prior to and continued after the first dose of the study drug. All prior and concomitant medications will be summarized by primary system organ class and preferred term. All prior/concomitant medications will be summarized as concomitant medications, and will not be included in prior medication outputs.

Surgical and medical procedures (non-drug therapies) will be summarized by primary system organ class and preferred term. All summaries will be on the safety set.

#### **2.4.3 Prior MS DMT treatment**

Number and percentage of patients on prior MS DMT treatments will be presented. Along with the number and percentage, the duration of previous MS DMTs before switching to Siponimod will also be presented. The MS DMT information will also be repeated on the subgroups if needed.

#### **2.5 Analysis of the primary objective**

The primary objective is to evaluate overall safety and tolerability profile of siponimod in advancing RMS patients who are converting from currently approved oral, injectable or infusion RMS DMTs.

The primary aim of this study is to evaluate the overall safety and tolerability profile of siponimod 2mg in patients with relapsing forms of MS.

### **2.5.1 Primary endpoint**

The primary endpoint is the occurrence of any study drug related treatment emergent adverse events during 6-month treatment period.

### **2.5.2 Statistical hypothesis, model, and method of analysis**

The number (and percentage) of patients with treatment emergent adverse events suspected to be related to study medication will be summarized by primary system organ class and preferred term.

The 95% exact binomial confidence interval for the overall rate of adverse event suspected to be related to study medication will be calculated.

A patient with multiple adverse events within a category (overall, primary system organ class, or preferred term) is only counted once towards the total of that category.

The analysis of the primary variable will also be stratified by prior MS DMTs. Along with the overall treatment emergent adverse events suspected to be related to study medication, a subgroup analysis by prior MS DMTs will also be provided.

Analysis of primary endpoint will be based on the Safety Set.

No formal hypothesis is being tested for the primary endpoint.

### **2.5.3 Handling of missing values/censoring/discontinuations**

No missing data will be imputed. All analyses will be using observed-case approach.

### **2.5.4 Sensitivity and Supportive analyses**

Neither sensitivity analysis nor supportive analysis is planned for the study.

## **2.6 Analysis of secondary objectives**

The following are the secondary objective(s) planned for the study:

1. To evaluate treatment satisfaction with siponimod in advancing RMS patients using outcomes based on the Treatment Satisfaction Questionnaire for Medication (TSQM-9).
2. To evaluate cardiac safety during siponimod treatment initiation
3. To evaluate treatment persistence with siponimod

All secondary analyses will also be based on the Safety Set.

### **2.6.1 Secondary endpoints**

#### **2.6.1.1 Treatment Satisfaction Questionnaire for Medication (TSQM-9)**

Please refer to [Section 2.10](#) for details.

#### **2.6.1.2 Change from Baseline in heart rate**

The change from Baseline in heart rate to 6 hours after 1st treatment will be summarized by number of observations, mean, standard deviation, minimum, 25th percentile, median, 75th percentile, and maximum.

The above analysis will also be performed on the subgroup of prior MS DMTs.

#### **2.6.1.3 Occurrence of any adverse events**

Refer to [Section 2.7.1](#) for details on the occurrence of any adverse events.

#### **2.6.1.4 Occurrence of hospitalizations**

Summary statistics will be provided for number of hospitalizations per patient occurred during treatment period. Number and percentages of patients having at least one hospitalization during treatment period will be provided.

#### **2.6.1.5 Patient retention**

The number of patients who complete the study will comprise patient retention. Number (and percentage) of patients completed study will be provided. Number of patients who are enrolled into the study, continued the study and discontinued the study will be presented.

### **2.6.2 Statistical hypothesis, model, and method of analysis**

No formal hypothesis is being tested for the secondary endpoint.

### **2.6.3 Handling of missing values/censoring/discontinuations**

No missing data will be imputed.

## **2.7 Safety analyses**

All safety analyses will be based on the Safety Set. Subgroup analysis will be performed on the AE tables as required.

### **2.7.1 Adverse events (AEs)**

The number (and percentage) of patients with treatment emergent adverse events (events started after the first dose of study medication to 30 days after the date of the last actual administration of any study treatment or events present prior to start of treatment but increased in severity based on preferred term) will be summarized.

AEs will be listed separately.

#### **Adverse events by System Organ Class and Preferred Term**

All adverse events starting on or after the first treatment will be coded utilizing the MedDRA version xx (during the database lock) dictionary, tabulated, and analyzed by primary system organ class and preferred term.

Primary system organ classes will be sorted alphabetically and, within each primary system organ class, the preferred terms will be sorted in descending order of frequency.

If a patient reported more than one adverse event with the same preferred term, the adverse event will be counted only once. If a patient reported more than one adverse event within the same primary system organ class, the patient will be counted only once at the system organ class level.

All adverse events will also be summarized by Standardized MedDRA Query (SMQ) and preferred term.

